10.3. Criteria for Potentially Clinically Significant Values (PCSV)

Parameter	PCSV
Clinical chemistry	
ALT	By distribution analysis: >2 ULN and baseline ≤ 2 ULN >3 ULN and baseline ≤ 3 ULN >5 ULN and baseline ≤ 5 ULN >10 ULN and baseline ≤ 10 ULN >20 ULN and baseline ≤ 20 ULN
AST	By distribution analysis: >2 ULN and baseline ≤ 2 ULN >3 ULN and baseline ≤ 3 ULN >5 ULN and baseline ≤ 5 ULN >10 ULN and baseline ≤ 10 ULN >20 ULN and baseline ≤ 20 ULN
Alkaline Phosphatase	> 1.5 ULN and baseline ≤ 1.5 ULN
Total Bilirubin	> 1.5 ULN and baseline ≤ 1.5 ULN > 2 ULN and baseline ≤ 2 ULN
Conjugated bilirubin	> 35% total bilirubin (when total bilirubin >1.5 ULN)
ALT and Total Bilirubin	ALT > 3 ULN and Total Bilirubin > 2 ULN and baseline ALT≤3 ULN or Total bilirubin ≤ 2 ULN
CPK	> 3 ULN and ≤ 5 ULN and baseline ≤ 3ULN >5 ULN and ≤ 10 ULN and baseline ≤ 5 ULN >10 ULN and baseline ≤ 10 ULN
Creatinine	≥ 150 µmol/L (adults) ≥ 30% from baseline ≥ 100% from baseline
CrCl (mL/min) (Estimated creatinine clearance based on the Cokcroft-Gault equation)	≥15 - <30 (severe decrease in GFR) ≥30 - < 60 (moderate decrease in GFR) ≥60 - <90 (mild decrease in GFR) ≥ 90 (normal GFR)
eGFR (mL/min/1.73m ²) (Estimate of GFR based on an MDRD equation)	≥15 - <30 (severe decrease in GFR) ≥30 - < 60 (moderate decrease in GFR) ≥60 - <90 (mild decrease in GFR) ≥ 90 (normal GFR)

Parameter	PCSV
Uric Acid	
Hyperuricemia:	>408 µmol/L
Hypouricemia:	<120 µmol/L
Blood Urea Nitrogen	≥17 mmol/L
Chloride	<80 mmol/L ≥115 mmol/L
Sodium	≤129 mmol/L ≥ 160 mmol/L
Potassium	< 3 mmol/L ≥ 5.5 mmol/L
Glucose	
Hypoglycaemia	≤ 3.9 mmol/L and < LLN
Hyperglycaemia	≥ 7 mmol/L (fasted); ≥ 11.1 mmol/L (unfasted)
HbA1c	>8%
Albumin	≤25 g/L
CRP	> 2 ULN or ≥10 mg/L, if ULN not provided
Hematology	
WBC	< 3.0 Giga/L (3000/ mm ³) (Non-Black) < 2.0 Giga/L (2000/ mm ³) (Black) ≥16.0 Giga/L (16000/ mm ³)
Lymphocytes	>4.0 Giga/L
Neutrophils	< 1.5 Giga/L (1500/ mm ³) (Non-Black) < 1.0 Giga/L (1000/ mm ³) (Black)
Monocytes	>0.7 Giga/L
Eosinophils	> 0.5 Giga/L (500/ mm ³) or > ULN if ULN ≥ 0.5 Giga/L
Hemoglobin	≤115 g/L (Male); ≤95 g/L (Female) ≥185 g/L (Male); ≥165 g/L (Female) Decrease from Baseline ≥15 g/L Decrease from Baseline ≥20 g/L
Hematocrit	≤0.37 v/v (Male) ; ≤0.32 v/v (Female) ≥0.55 v/v (Male) ; ≥0.5 v/v (Female)
RBC	≥6 Tera/L

Parameter	PCSV
Platelets	< 100 Giga/L (100 000/mm ³) ≥700 Giga/L (700000/mm ³)
Urinalysis	
pH	≤4.6 ≥8
Vital signs	
HR	≤ 50 bpm and decrease from baseline ≥ 20 bpm ≥ 120 bpm and increase from baseline ≥ 20 bpm
SBP	≤ 95 mmHg and decrease from baseline ≥ 20 mmHg ≥ 160 mmHg and increase from baseline ≥ 20 mmHg
DBP	Young and elderly patients ≤ 45 mmHg and decrease from baseline ≥ 10 mmHg ≥ 110 mmHg and increase from baseline ≥ 10 mmHg
Weight	≥5% increase versus baseline ≥5% decrease versus baseline
ECG parameters	
HR	≤ 50 bpm and decrease from baseline ≥ 20 bpm ≥ 120 bpm and increase from baseline ≥ 20 bpm
PR	≥220 ms and increase from baseline ≥20 ms
QRS	≥ 120 ms
QTc Borderline Prolonged* Additional	Absolute values (ms) Borderline 431-450 ms (Male) 451-470 ms (Female) Prolonged* > 450 ms (Male) > 470 ms (Female) QTc ≥500 ms Increase versus baseline (Males and Females) Borderline Δ 30-60 ms Prolonged * Δ > 60 ms

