6.2.2. Exclusion Criteria

A patient who meets any of the following criteria will be excluded from the study:

1. A hospital or clinic discharge diagnosis of acute pancreatitis within 12 weeks of screening
2. Lipid apheresis or plasma exchange treatment within the last 4 weeks or plans to undergo apheresis or plasma exchange during the time frame of the study
3. History of class 3/4 heart failure at any time in the past, or hospitalization for heart failure, diagnosis of a myocardial infarction, stroke, TIA, unstable angina, CABG, PCI, carotid surgery/stenting within 3 months before the screening visit
4. History of bleeding disorders, esophageal varices, heparin induced thrombocytopenia, or contraindications to receiving heparin (eg, allergic reaction to heparin)
5. New clinically significant findings on 12-lead electrocardiogram (ECG) that would place the patient at risk or interfere with participation in the study
6. Dose(s) of any permitted concomitant medications that have changed in the time period prior to screening as described in Section 7.8.2
7. Presence of any clinically significant uncontrolled endocrine disease known to influence serum lipids or lipoproteins

NOTE: Patients on thyroid replacement therapy are eligible if the dosage of thyroxine has been stable for at least 12 weeks prior to screening visit

8. Use of systemic corticosteroids, unless used as replacement therapy for pituitary/adrenal disease (in which case must be a stable regimen for at least 6 weeks prior to the screening visit)
NOTE: Topical, intra-articular, nasal, inhaled and ophthalmic steroid therapies are not considered as 'systemic' and are allowed
9. Calculated eGFR <45 ml/min (according to 4-variable MDRD study equation)
10. History of drug or alcohol abuse (including binge drinking which typically involves consumption of approximately 4 drinks for women and 5 drinks for men in a few hours) within 1 year of screening
11. Exposure to another investigational drug or therapy within 30 days or within at least 5 half-lives (whichever is longer) prior to the screening visit
12. Blood donation of any volume within 1 month prior to administration of study drug
13. Known hypersensitivity to monoclonal antibody therapeutics. Known sensitivity to any of the components of the investigational product formulation

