8.2.5.3. Electrocardiogram

Electrocardiograms should be performed before blood is drawn during visits requiring blood draws. A standard 12-lead ECG will be performed at time points according to [Table 1](#). A 12-lead ECG should be performed in the supine position after resting for at least 10 minutes. For each ECG recording throughout the study, the electrodes should be positioned in the same place as much as possible. The ECG will be interpreted locally by the investigator. Heart rate will be recorded from the ventricular rate, and the PR, QRS, RR, QTcB and QTcF intervals will be recorded. Any clinically significant abnormality should be documented as an AE/SAE as applicable. Each ECG tracing will be analyzed in comparison with the screening record trace. The ECG strips or reports will be retained with the source.

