5.8. Analysis of Safety Data

The summary of safety results will be presented separately for the DBTP and SBTP, unless otherwise noted. Safety summaries for the DBTP will be presented by treatment groups (evinacumab, placebo), as well as by treatment group within each cohort containing patients from the double-blind safety analysis set. Safety summaries for the SBTP will be presented by all patients and by treatment group in DBTP (i.e., evinacumab, placebo), for patients in the single-blind safety analysis set. No formal inferential testing will be performed for either period. Summaries will be descriptive in nature.

General common rules

All safety analyses will be performed, unless otherwise specified, using the following common rules:

- Safety data in patients who do not belong to the safety analysis set (i.e., exposed but not randomized) will be listed separately.
- PCSV values are defined as abnormal values considered medically important by the Sponsor according to predefined criteria/thresholds based on literature review and defined by the Sponsor for clinical laboratory tests and vital signs (PCSV version dated January 2009 [[Appendix 10.3](#)]). Considering that the threshold defined in the PCSV list for monocytes and basophils can be below the ULN, the following PCSV criterion will be used for the PCSV analysis of monocytes and basophils:
 - PCSV criterion for monocytes: >0.7 Giga/L or $>\text{ULN}$ (if $\text{ULN} \geq 0.7$ Giga/L).
 - PCSV criterion for basophils: >0.1 Giga/L or $>\text{ULN}$ (if $\text{ULN} \geq 0.1$ Giga/L).
- PCSV criteria will determine which patients had at least 1 PCSV during the respective TEAE periods, taking into account all evaluations including unscheduled or repeated evaluations.
- For summary tables, only protocol scheduled measurements (as defined by e-CRF visit label) will be included. Patient listings will include all measurements, scheduled and unscheduled.
- The treatment-emergent PCSV denominator by treatment group for a given parameter will be based on the number of patients assessed for that given parameter at least once during the respective TEAE periods.
- For quantitative safety parameters including central laboratory measurements and vital sign scores, descriptive statistics will be used to summarize observed values and change from baseline values by visit.

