5.8.5. Clinical Laboratory Measurements

For respective treatment period (DBTP and SBTP), clinical laboratory parameter actual values (quantitative) and change from baseline values will be descriptively summarized at baseline and each post-baseline visit (collected up to the day of last dose of study treatment +28 days) by at least patient number, mean, median, Q1, Q3, SD, minimum and maximum. Clinical laboratory parameters mean changes from baseline, with the corresponding SE, can be plotted at each visit in the case results warrant further investigation. These parameters will be presented by the biological functions defined in Section 4.8.2. For glucose, only fasting samples will be included in the summaries.

Individual patient laboratory parameter measurements will be additionally evaluated by PCSV criteria (See [Appendix 10.3](#)), specifically identifying patients with at least one post-baseline

measurement that meets the PCSV criteria within the respective TEAE periods. These laboratory parameters will be presented by the biological functions defined in Section 4.8.2. The incidence of PCSVs at any time during the respective TEAE periods will be summarized regardless of the baseline level, and again according to the following baseline categories:

- Normal (according to PCSV criterion/criteria)/missing
- Abnormal according to PCSV criterion or criteria

Patient listings of laboratory measurements that meet PCSV criteria will be provided for the report appendix. For those laboratory parameters that don't have an associated PCSV criteria, similar summary tables can be provided based on measurements outside the central laboratory normal ranges, if applicable.

Drug-induced liver injury

For respective treatment period (DBTP and SBTP), an evaluation of drug-induced serious hepatotoxicity (eDISH) with the graph of distribution of peak values of ALT versus peak values of total bilirubin will also be presented using post-baseline values during respective TEAE periods. Note that the ALT and total bilirubin values are presented on a logarithmic scale. The graph will be divided into 4 quadrants with a vertical line corresponding to 3 x ULN for ALT and a horizontal line corresponding to 2 x ULN for total bilirubin.

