5.8.7. Analysis of 12-Lead ECG

For respective treatment period (DBTP and SBTP), ECG parameters will be described through an overall interpretation of ECG status (e.g. normal, abnormal [clinically significant (Yes/No)]). The count and percentage of patients with at least 1 abnormal post-baseline ECG during the respective TEAE period will be summarized according to the following baseline status categories:

- Normal/missing;
- Abnormal

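### The GFR rows of the SAP's PCSV appendix list normal function as a PCSV and have no band below 15, and its ECG interval criteria are used by no planned analysis

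*SAP*

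**What the plan says.** **Renal rows.** SAP Appendix 10.3 gives CrCl and eGFR identical entries in the PCSV column: "≥15 - <30 (severe decrease in GFR"), then 30 to under 60 (moderate), 60 to under 90 (mild), and finally "≥ 90 (normal GFR"). Neither row has an entry below 15, and neither carries a condition on the baseline value.

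**How PCSVs are defined and counted.** SAP 5.8 states that "PCSV values are defined as abnormal values considered medically important by the Sponsor", using thresholds "defined by the Sponsor for clinical laboratory tests and vital signs". SAP 5.8.5 counts a patient who has at least one post-baseline value meeting a criterion. It adds that "The incidence of PCSVs at any time during the respective TEAE periods will be summarized regardless of the baseline level", and then again by baseline category: normal by the PCSV criteria or missing, versus abnormal by those criteria.

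**Renal entry limit.** Protocol 6.2.2 excludes patients with "Calculated eGFR <45 ml/min (according to 4-variable MDRD study equation").

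**ECG.** Appendix 10.3 also lists criteria for HR, PR, QRS and QTc. Protocol 8.2.5.3 has heart rate taken from the ECG and says that "the PR, QRS, RR, QTcB and QTcF intervals will be recorded". SAP 4.8.4 reduces the ECG to normal or abnormal. SAP 5.8.7 says that "ECG parameters will be described through an overall interpretation of ECG status", with a clinical-significance flag for abnormal tracings, and tabulates abnormal post-baseline ECGs by baseline status.

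**The concern.** A PCSV table should show how many patients moved into a range that matters. A row that includes the normal range and omits the lowest range cannot do that. Patients with no change would be counted, and the lowest values would appear in no GFR category.

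The rows matter because Protocol 10.4.5.2 commits to reporting the number and percentage of patients with a laboratory PCSV. In the cohort 1 interim analysis (SAP section 7), PCSV tables are the only general laboratory output, so no by-visit laboratory summary would sit beside a faulty row.

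The ECG rows raise a different question. Thresholds are specified and the intervals are collected, but nothing links the two. A reader of the SAP cannot tell whether interval outliers will be reported.

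**Working it through.** The plan states no figure here that could be reproduced. The check classifies values by the printed bands, tests what else in the table would catch a low value, and looks for any analysis that uses the ECG rows.

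**Step 1. Classify values by the four printed bands (CrCl and eGFR alike).**

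| Value | Band met |
|---|---|
| 5, 10, 14.9 | none |
| 15, 29.9 | severe |
| 30, 45, 59.9 | moderate |
| 60, 89.9 | mild |
| 90, 120 | normal |

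Every value of 15 or more meets a listed criterion, and no value below 15 does.

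**Step 2. Apply the baseline split in SAP 5.8.5.** Entry requires eGFR of at least 45. A patient whose baseline is still 15 or more meets a band at baseline, so is abnormal by the PCSV criteria, even at 95. SAP 6.3 places missing baselines in the normal/missing stratum. For eGFR, that stratum would therefore hold essentially only patients with no baseline value. A patient who enters at 45 to 59 and stays there is counted as a moderate decrease.

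Treating each band as its own criterion does not repair this. A rise from 55 to 65 would then count as newly entering the mild band, and a rise from 85 to 92 as newly entering the normal one.

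**Step 3. Does anything else in the table catch a fall below 15?** Appendix 10.3 lists creatinine at 150 µmol/L or more, at least 30% from baseline, and at least 100% from baseline. Take eGFR as proportional to creatinine^(−k), with the patient's other inputs fixed. The documents do not give k, so 1.0 to 1.5 is an assumption. For a fall from 45 to 15, the creatinine ratio is (45/15)^(1/k):

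- k = 1.0: 3.0 times baseline
- k = 1.2: 2.5 times baseline
- k = 1.5: 2.1 times baseline

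All exceed 2.0, so the 100% criterion is met, and with it the 30% one. A higher start or a lower end gives a larger ratio.

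The 30% criterion also leaves room if the baseline has drifted below 45 since screening. It is met for a fall to 15 from any baseline of at least 15 × 1.3^k. That is 19.5 at k = 1.0 and 15 × 1.482 = 22.2 at k = 1.5.

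**Step 4. Are the GFR rows tabulated?** SAP 5.8.5 presents PCSVs by the biological functions in SAP 4.8.2. That section lists creatinine, BUN and uric acid under renal function, and not CrCl or eGFR. The chemistry panel in Protocol 8.2.5.4 names neither. The SAP does not settle the question.

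**Step 5. Is any analysis tied to the ECG rows?**

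- SAP 5.8 confines PCSVs to laboratory tests and vital signs.
- SAP 4.8.4 and 5.8.7 use the overall reading.
- SAP 6.4 mentions ECG and PCSVs together, but only as a permissive rule about unscheduled measurements.

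No section applies the HR, PR, QRS or QTc thresholds. The QTc row also does not say whether QTcB or QTcF is meant.

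**The case against.** **The renal signal is not lost.** A reader might infer that the PCSV table would miss a collapse in renal function. The documents do not support that. Step 3 shows that the creatinine criteria flag an eligible patient who falls below 15, and BUN has its own threshold of 17 mmol/L. This objection stands, and it limits the point to a mis-specified table.

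**The rows may not be used.** A reader might also infer that the renal output would be filled with unchanged patients. Because SAP 4.8.2 does not name CrCl or eGFR, that is not established. This stands too, but rows of uncertain status in a pre-specified appendix still need to be settled.

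**The top band may be a reference category.** The definition in SAP 5.8 requires an abnormal value, so a band labelled normal is most naturally a reference level. On that reading a patient at 95 is not counted, and a stable patient at 45 to 59 falls in the abnormal-at-baseline stratum. This is plausible, but the SAP never says so, and the reading does not supply the missing band below 15.

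**ECG findings are reported elsewhere.** It is tempting to say that a new QTc of 500 ms or more in a patient with an already abnormal baseline ECG would not show. That goes too far. SAP 5.8.7 carries a clinical-significance flag. Protocol 8.2.5.3 compares each tracing with the screening trace and requires clinically significant abnormalities to be recorded as adverse events. What remains is that, in the planned count by baseline status, such a patient sits in the same abnormal/abnormal cell as one with no change.

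**Materiality.** The important potential risks in Protocol 3.2.1 are hypersensitivity, immunogenicity and embryofetal toxicity. Renal and QT events are not among the events of special interest, and the safety analysis is descriptive. This supports a low rating.

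**Conclusion.** The point holds as a minor safety-reporting defect. As written, the CrCl and eGFR rows conflict with the SAP's own definition of a PCSV. All values of 15 or more meet a GFR criterion, no value below 15 does, and the baseline split does not work for these rows. The HR, PR, QRS and QTc criteria belong to no planned analysis although the measurements are recorded. Neither defect hides a safety signal: creatinine covers the renal event, and adverse event reporting covers clinically significant ECG changes. The primary endpoint is unaffected.

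This rests on three assumptions:

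- The appendix table was read correctly from the PDF. The same gap appears in both GFR rows while other less-than entries in the table survive.
- The exponent k lies between 1.0 and 1.5.
- Baseline eGFR is close to the screening value used for entry. The entry limit is on eGFR, so the creatinine argument carries over to CrCl only in so far as a patient's CrCl is similar.

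**What to change.** **Appendix 10.3, CrCl and eGFR.** Add a category for values below 15. Mark 90 and above as a reference category that is not counted as a PCSV. Present both measures as a shift table from baseline band to worst post-baseline band, for each treatment period. The ALT, AST, alkaline phosphatase, total bilirubin and CPK rows already carry baseline conditions, so relating the result to baseline follows the appendix's own practice.

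**SAP 4.8.2.** Name CrCl and eGFR under renal function, so that it is clear they are derived and tabulated.

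**SAP 5.8.7.** Either apply the Appendix 10.3 ECG criteria to the recorded heart rate and intervals, stating QTcB or QTcF, and extend the PCSV scope in SAP 5.8 to ECG; or delete the ECG rows. Either resolves the inconsistency.

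**Cost.** A short SAP edit and at most two small additional tables, from data the protocol already collects. No change to study conduct is needed.

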10.4. Schedule of Time and Events

Table 1: Schedule of Events

Study Procedure	Screening Period			Placebo run-in ¹ / Baseline		Double-Blind Treatment Period ²							Single-Blind Treatment Period ³		
	Visit 1	Visit 1b ⁴	Visit 2	Visit 3	Visit 4	Visit 5	Visit 6	Visit 7	Visit 8	Visit 9	Visit 10 ⁵	Visit 11	Visit 12	End of Treatment Visit 13	
Day	-66 to -59	-58 to -52	-51 to -39	-28 +4d	-14 ± 4d	1 ± 4d	15 ± 4d	29 ± 4d	43 ± 4d	57 ± 4d	85 ± 4d	113 ± 4d	141 ± 4d	169 ± 5d	
Week					0	2	4	6	8	12	16	16	20	24	
Screening/Baseline:															
Inclusion/Exclusion	X		X	X											
Informed Consent	X														
Medical History ⁶	X														
Demographics	X														
FT4, TSH	X														
FSH (for women only)	X														
PT/PTT, INR	X														
Cohort Assignment			X												
Randomization					X										
Treatment:															
Heparin ⁷			X ⁸												X
Administer Placebo				X ^{9,10}											
Administer Study Drug (evinacumab or placebo)					X ^{9,10}		X ^{9,10}		X ^{9,10}		X ^{9,10}				
Administer evinacumab											X ^{9,10}	X ^{9,10}	X ^{9,10}		
Concomitant Medications and treatment	X		X	X	X	X	X	X	X	X	X	X	X	X	X
Efficacy:															
Lipids and lipoproteins ^{11,12}	X ¹³	X ¹³		X	X	X	X	X	X	X	X	X	X	X	X
HbA1c, Insulin, C-peptide, and Homa ¹¹				X		X						X			X
Post-heparin LPL, endothelial lipase (EL), hepatic lipase (HL) activity assay and HL mass assay ¹¹			X ¹⁴												X
Pre-heparin LPL and EL mass assay ¹¹			X												X
Train/dispense ePRO device			X												
Daily Symptom Questionnaire				X		X ¹⁶		X ¹⁶		X ¹⁶	X ¹⁶	X ¹⁶	X ¹⁶	X ¹⁶	X ¹⁶

Study Procedure	Screening Period			Placebo run-in ¹ / Baseline		Double-Blind Treatment Period ²							Single-Blind Treatment Period ³		
	Visit 1	Visit 1b ⁴	Visit 2	Visit 3	Visit 4	Visit 5	Visit 6	Visit 7	Visit 8	Visit 9	Visit 10 ⁵	Visit 11	Visit 12	End of Treatment Visit 13	
Day	-66 to -59	-58 to -52	-51 to -39	-28	-14 ± 4d	1 ± 4d	15 ± 4d	29 ± 4d	43 ± 4d	57 ± 4d	85 ± 4d	113 ± 4d	141 ± 4d	169 ± 5d	
Week						0	2	4	6	8	12	16	20	24	
(Hypertriglyceridemia and Acute Pancreatitis Signs and Symptoms) ¹⁵															
Symptom/Dietary Impact Questionnaire (Hypertriglyceridemia and Acute Pancreatitis Dietary Behavior) ¹⁵				X		X ¹⁶		X ¹⁶		X ¹⁶	X ¹⁶	X ¹⁶	X ¹⁶	X ¹⁶	
Site review of questionnaires for compliance				X		X		X		X	X	X	X	X	
Safety:															
Vital Signs	X		X	X ¹⁰	X	X ¹⁰	X	X ¹⁰	X	X ¹⁰	X ¹⁰	X ¹⁰	X ¹⁰	X	
Physical Examination	X			X		X					X			X	
Weight	X		X	X	X	X	X	X	X	X	X	X	X	X	
Electrocardiogram ¹⁷	X				X						X			X	
Adverse Events ¹⁸	X	X	X	X	X	X	X	X	X	X	X	X	X	X	
Confirm required contraception use and reminder of pregnancy status reporting in women of child bearing potential and female partners of male patients ¹⁹	X	X	X	X	X	X	X	X	X	X	X	X	X	X	
Laboratory Testing:															
Hematology ¹¹	X			X		X	X	X	X	X	X	X	X	X	
Blood Chemistry ¹¹	X			X		X	X	X	X	X	X	X	X	X	
Pregnancy Test	serum		urine		urine		urine		urine	urine	urine	urine	urine	serum	
Urinalysis	X		X		X					X				X	
Imaging and Other Assessments:															
DW-MRI ²⁰				X	X						X			X	
¹⁸ F-FDG-PET ²⁰					X						X				
PK/Drug Concentration and ADA Samples:															
PK/Drug conc. Sample ²¹						X ²²		X ²²		X ²²	X ²²		X ²²	X	
ADA sample						X		X			X			X	
Biomarkers:															
Biomarker serum/plasma				X	X	X	X	X	X	X	X	X	X	X	
Amylase, lipase ¹¹	X		X	X	X	X	X	X	X	X	X	X	X	X	

Study Procedure	Screening Period			Placebo run-in ¹ / Baseline		Double-Blind Treatment Period ²							Single-Blind Treatment Period ³		
	Visit 1	Visit 1b ⁴	Visit 2	Visit 3	Visit 4	Visit 5	Visit 6	Visit 7	Visit 8	Visit 9	Visit 10 ⁵	Visit 11	Visit 12	End of Treatment Visit 13	
Day	-66 to -59	-58 to -52	-51 to -39	-28	-14 ± 4d	1 ± 4d	15 ± 4d	29 ± 4d	43 ± 4d	57 ± 4d	85 ± 4d	113 ± 4d	141 ± 4d	169 ± 5d	
Week						0	2	4	6	8	12	16	20	24	
APOC2, APOC3, APOA5, NEFA ¹¹						X					X			X	
Inflammation Panel (eg, IL-1, IL-6, IL-8, TNF α)				X		X					X			X	
hs-CRP				X		X					X			X	
Lipid sub-fractions by UC						X					X			X	
Genomic DNA sample:															
Whole blood DNA sample				X											

Schedule of Events (continued)

Study Procedure	Off-Drug Treatment Follow-Up Period				
	Visit 14	Phone Call	Visit 16	Phone Call	End of Study Visit 18
Day	197± 5d	225± 5d	253± 5d	281± 5d	309± 5d
Week(s)	28	32	36	40	44
Treatment:					
Concomitant Medications and treatment	X	X	X	X	X
Efficacy:					
Lipids and lipoproteins ^{11,12}	X		X		X
HbA1c, Insulin, C-peptide, and Homa ¹¹					X
Daily Symptom Questionnaire (Hypertriglyceridemia and Acute Pancreatitis Signs and Symptoms) ¹⁵	X ¹⁶		X ¹⁶		X ¹⁶
Symptom/Dietary Impact Questionnaire (Hypertriglyceridemia and Acute Pancreatitis Dietary Behavior) ¹⁵	X		X		X
Site review of responses to questionnaires	X		X		X
Safety:					
Vital Signs	X		X		X
Physical Examination					X
Weight	X		X		X
Electrocardiogram ¹⁷					X
Adverse Events	X	X	X	X	X
Confirm required contraception use and reminder of pregnancy status reporting in women of child bearing potential and female partners of male patients ¹⁹	X	X	X	X	X
Laboratory Testing:					
Hematology ¹¹	X		X		X
Blood Chemistry ¹¹	X		X		X
Pregnancy Test ¹⁹	Urine	Urine	urine	urine	serum
Urinalysis					X
Imaging and Other Assessments:					
Amylase, lipase ¹¹	X		X		X
PK/Drug Concentration and ADA Samples:					
PK/Drug conc. Sample ²¹	X		X		X
ADA sample 23					X
Biomarkers:					
Inflammation Panel (eg, IL-1, IL-6, IL-8, TNF α)					X
hs-CRP					X

